9.4.1.3 Key secondary objective (Overall survival)

OS (mITT) is a key secondary endpoint of this study. OS is defined as the time from the date of randomisation until death due to any cause. Any participant not known to have died at the time of analysis will be censored based on the last recorded date on which the participant was known to be alive.

Note: Survival calls will be made in the week following the date of DCO for the analysis (these contacts should generally occur within 7 days of the DCO). If participants are confirmed to be alive or if the death date is after the DCO date, these participants will be censored at the date of DCO. Death dates may be found by checking publicly available death registries.

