9.5 Statistical analyses

All personnel involved with the analysis of the study will remain blinded until database lock and Clinical Study Protocol deviations identified.

Analyses will be performed by AstraZeneca or its representatives. A comprehensive statistical analysis plan will be developed and finalised before database lock and will describe the participant populations to be included in the analyses and the procedures to account for missing, unused, and spurious data. This section is a summary of the planned statistical analyses of the primary and secondary endpoints. Any deviations from this plan will be reported in the CSR.

Depending on the extent of any impact, summaries of data relating to participants diagnosed with COVID-19, and impact of COVID-19 on study conduct (in particular missed visits, delayed or discontinued IP, and other protocol deviations) may be generated. Relevant listings will be generated as needed. More details will be provided in the SAP.

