3.2.2.1 Overall survival

Overall survival (OS) is a key secondary endpoint for this study. OS is defined as the time from the date of randomisation until death due to any cause regardless of whether the patient withdraws from randomised therapy or receives another anti-cancer therapy (i.e. date of death or censoring – date of randomisation + 1). Any patient not known to have died at the time of analysis will be censored based on the last recorded date on which the patient was known to be alive (SUR_DAT, recorded within the SURVIVE module of the eCRF).

Note: Survival calls will be made in the week following the date of DCO for the analysis (these contacts should generally occur within 7 days of the DCO). If patients are confirmed to be alive or if the death date is after the DCO date, these patients will be censored at the date of DCO. The status of ongoing, withdrawn (from the study) and “lost to follow-up” patients at the time of the final OS analysis should be obtained by the site personnel by checking the patient’s notes, hospital records, contacting the patient’s general practitioner and checking publicly available death registries. If the patient has actively withdrawn consent to the processing of their personal data, the vital status of the patient can be obtained by site personnel from publicly available resources where it is possible to do so under applicable local laws.

If a patient is known to have died where only a partial death date is available, then the date of death will be imputed as the latest of the last date known to be alive + 1 from the database and the imputed death date derived using the following information:

- a. For missing day only – using the 1st of the month
- b. For missing day and month – using the 1st of January

If there is evidence of death but the date is entirely missing, it will be treated as missing, i.e., censored at the last known alive date.

Note that for any OS analysis performed prior to the final OS analysis, in the absence of survival calls being made, it may be necessary to use all relevant CRF fields to determine the last recorded date on which the patient was known to be alive for those patients still on-treatment (since the SURVIVE module is only completed for patients off treatment if a survival sweep is not performed). The last date for each individual patient is defined as the

latest date recorded on the CRFs. This includes, but is not limited to, the following dates recorded on the CRF:

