4.1.4 Imputation rules

Missing safety data will generally not be imputed. However, safety assessment values of the form of “< x” (i.e., below the lower limit of quantification) or > x (i.e., above the upper limit of quantification) will be imputed as “x” in the calculation of summary statistics but displayed as “< x” or “> x” in the listings. Additionally, AEs that have missing causality (after data querying) will be assumed to be related to study drug. Missing CTCAE grades will not be imputed.

Patients with a partial date of birth (i.e. for those countries where year of birth only is given) will have an assumed date of birth of 1st Jan [given year]) for calculation of age at informed consent.

Partial dates for the following modules will be imputed: prior cancer therapy, previous radiotherapy and prior and concomitant medications and adverse events, as well as for other modules, where required.

The original incomplete or missing dates will be presented in the listings.

Adverse events and medications

Adverse events: all AEs will be considered as treatment-emergent unless the opposite can be clearly stated. Imputation will be done only in the context of identifying TEAEs.

Medications/therapies: all medications will be considered as concomitant unless the opposite can be clearly stated.

In practice, for adverse events and medications, original incomplete or missing start dates will be imputed as below:

- Missing day: impute the 1st of the month unless month and year are the same as month and year of first dose of study drug then impute first dose date;
- Missing day and month: impute 1st January unless year is the same as first dose date then impute first dose date;
- Completely missing: impute first dose date unless the end date suggests it could have started prior to this in which case impute the 1st January of the same year as the end date.

When imputing a start date, ensure that the new imputed date is sensible, i.e., is prior to the end date of the AE or medication.

Original incomplete or missing stop dates for adverse events and medications/therapies will be imputed as below:

- Missing day: impute the last day of the month;
- Missing day and month: impute 31st December. Flags will be retained in the database indicating where any programmatic imputation has been applied, and in such cases, any durations would not be calculated.

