Overall survival	
Stratified log-rank test for:
 
 
• Secondary analysis 
• Sensitivity analysis using alternative censoring rules – attrition bias 
• Analysis accounting for COVID-19 deaths 
Analysis in the presence of non-proportional hazards assumption – Stratified Max-combo test
 
Additional analysis using Cox proportional hazards models to determine the effect of covariates on the HR estimate
 
Subgroup analysis using Cox proportional hazards model

Additional analysis using Cox proportional hazards model to determine the consistency of treatment effect between stratification factors via the approach of [Gail and Simon 1985](#).

Proportion of patients alive at 12 and 24 months from randomisation	KM estimates of survival at 12 and 24 months
Objective response rate	Logistic regression for: 
 • Secondary analysis using BICR tumour RECIST 1.1 data • Sensitivity analysis using study site Investigator tumour RECIST 1.1 data
Duration of response	KM estimates for DoR using BICR tumour data
Progression-free survival at 12 and 18 months from randomisation	KM estimates of progression-free survival at 12 and 18 months
Time from randomisation to second progression ^a	Stratified log-rank test
Time to death or distant metastasis	Stratified log-rank test using site BICR tumour RECIST 1.1 data
Time to first subsequent therapy or death	Stratified log-rank test
Time to second subsequent therapy or death	Stratified log-rank test
Symptom improvement rate (EORTC QLQ-C30 and QLQ-LC13 endpoints)	Logistic regression for symptom improvement
HRQoL/Function improvement rate (EORTC QLQ-C30 endpoints)	Logistic regression for HRQoL/Function improvement
Time to HRQoL/Function deterioration (EORTC QLQ-C30 endpoints)	Stratified log-rank test and KM estimate plots
Time to symptom deterioration (EORTC QLQ-C30 and QLQ-LC13 endpoints)	Stratified log-rank test and KM estimate plots
Change from baseline in key symptoms (EORTC QLQ-C30 and QLQ-LC13)	Mixed model repeated measures analysis

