4.2.2 Secondary efficacy endpoints

4.2.2.1 Overall survival

The key secondary endpoint of OS will be analysed using a stratified log-rank test, using the same methodology as described for the primary PFS endpoint. The effect of durvalumab versus placebo will be estimated by the HR together with its corresponding (1 – alpha adjusted) % CI and p-value. Kaplan-Meier plot of OS will be presented by treatment arm.

The stratification variables in the statistical modelling will be based on the values entered into Interactive voice response system (IVRS) at randomisation, even if it is subsequently discovered that these values were incorrect. Sensitivity analysis might be performed based on the values in the eCRF page if more than 10% randomised patients have discrepancies in stratification factors between IVRS and eCRF data.

Summaries of the number and percentage of patients who have died, those still in survival follow-up, those lost to follow-up, and those who have withdrawn consent will be provided along with the median OS for each treatment.

This analysis will be repeated on the ITT set.

The assumption of proportionality will be assessed in the same way as for PFS.

Overall survival status will also be listed.

Sensitivity analyses

A sensitivity analysis for OS will examine the censoring patterns to rule out attrition bias, achieved by a Kaplan-Meier plot of time to censoring where the censoring indicator of OS is reversed.

Proportional hazards will be tested firstly by examining plots of complementary log-log (event times) vs log (time) and, if these raise concerns, by fitting a time-dependent covariate to assess the extent to which this represents random variation.

The stratified Max-combo test will be conducted as a sensitivity analysis on OS, to test for treatment differences in the case of non-proportional hazards. The same algorithm as specified in [section 4.2.1](#) for PFS will be used. This analysis will be repeated on the ITT set.

The number of patients prematurely censored will be summarised by treatment arm. A patient would be defined as prematurely censored if their survival status was not defined at the DCO.

In addition, duration of follow-up will be summarised using medians:

- In censored patients who are alive at DCO only: Time from randomisation to date of censoring (date last known to be alive) for each arm.

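### SAP 3.2.2.1 censors a patient with evidence of death when the death date is wholly missing, and no defined OS analysis counts such deaths (minor)

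*SAP*

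**What the plan says.** Protocol 9.4.1.3 defines OS as time from randomisation to death from any cause and censors those whose death is not known: "Any participant not known to have died at the time of analysis will be censored based on the last recorded date" on which they were known to be alive. SAP 3.2.2.1 repeats this and then treats two kinds of incomplete death date differently.

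- Partial date: the death stays an event, and "the date of death will be imputed as the latest of the last date known to be alive + 1" and a date built from what is known. If only the year is known: "For missing day and month – using the 1st of January".
- No date at all: "If there is evidence of death but the date is entirely missing, it will be treated as missing, i.e., censored". The censoring date is that of last known survival.

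SAP 4.1.4 repeats the partial-date rule and does not mention a wholly missing date.

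On sensitivity analyses, the OS row of SAP Table 9 lists "Sensitivity analysis using alternative censoring rules – attrition bias". The matching text in SAP 4.2.2.1 reads: "A sensitivity analysis for OS will examine the censoring patterns to rule out attrition bias". It does so by a Kaplan-Meier plot with the OS censoring indicator reversed. The other OS sensitivity analyses in 4.2.2.1 are the stratified Max-combo test, a possible rerun with eCRF strata, and a COVID-19 analysis that censors further deaths. SAP 4.2.5.1 tabulates all deaths by arm whatever their date.

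**The concern.** Whether a death counts as an OS event depends on how much of its date was recorded. A patient with only a year is an event; a patient with no date leaves the risk set as if alive. For the second patient the rule applies only because there is evidence of death, so the assumption of non-informative censoring fails by construction.

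OS in the mITT set is the key secondary endpoint, tested under alpha control, and its information fraction is a count of OS events. The rule can lower that count, overstate OS24 in any arm with such deaths and, if the arms differ, shift the HR. As the plan is written, no OS estimate would show by how much.

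**Working it through.** **1. Which defined OS analyses count an undated death as an event?**

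- Main stratified log-rank and Cox analysis: no, by the sentence quoted from 3.2.2.1.
- Reversed-censoring plot: no; it describes censoring times and reclassifies nobody.
- Max-combo and eCRF-strata rerun: no; nothing in their descriptions changes the event flags.
- COVID-19 analysis: no; it removes deaths and adds none back.
- Deaths table: counts them, but is descriptive and gives no OS estimate.

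**2. How large could the effect be?** The plan has no figure to reproduce: the OS design HR, events and power are redacted, and no rate of undated deaths is given. Everything below is illustration on assumed inputs.

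Inputs: about 375 mITT patients at 2:1 (SAP 1.3), hence 250 and 125; median OS 47.5 and 29.1 months (earlier durvalumab study, Protocol 2.3.1). Assumed: exponential survival, uniform follow-up of 36 to 60 months, 1%, 2% or 5% of deaths undated, and a gap from last contact to death of 0–2 or 6–24 months. The model is an unstratified Cox model with one two-sided 5% log-rank test, over 6,000 simulated trials reused in every scenario (Monte Carlo SE of an HR difference 0.0003 or less).

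With all dates known: 209.8 deaths on average (125.3 durvalumab, 84.6 placebo), HR 0.6187, power 93.5%. Where two HRs are shown, they are for the short and the long gap.

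| Undated | Deaths affected | SAP rule | All as events at last alive + 1 | All as events at DCO |
|---|---|---|---|---|
| Both arms 1% | 2.1 | 0.6185 / 0.6180 | 0.6187 / 0.6188 | 0.6193 |
| Both arms 2% | 4.2 | 0.6185 / 0.6175 | 0.6187 / 0.6189 | 0.6200 |
| Both arms 5% | 10.5 | 0.6186 / 0.6161 | 0.6187 / 0.6191 | 0.6222 |
| Durvalumab only 1% | 1.3 | 0.6125 / 0.6135 | 0.6188 / 0.6202 | 0.6152 |
| Durvalumab only 2% | 2.5 | 0.6064 / 0.6083 | 0.6189 / 0.6217 | 0.6118 |
| Durvalumab only 5% | 6.3 | 0.5881 / 0.5928 | 0.6193 / 0.6261 | 0.6014 |
| Placebo only 1% | 0.8 | 0.6247 / 0.6233 | 0.6186 / 0.6173 | 0.6227 |
| Placebo only 2% | 1.7 | 0.6310 / 0.6280 | 0.6185 / 0.6160 | 0.6269 |
| Placebo only 5% | 4.2 | 0.6508 / 0.6429 | 0.6181 / 0.6119 | 0.6394 |

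**3. Check by hand.** Losing a share m of the events in an arm scales that arm's hazard by about (1 − m), so HR under the rule ≈ HR × (1 − m_durvalumab)/(1 − m_placebo). For 5% on durvalumab only: 0.6187 × 0.95 = 0.588 (simulated 0.5881, short gap). For 5% on placebo only: 0.6187/0.95 = 0.651 (simulated 0.6508). A separate simulation at HR 0.68 agreed: 2% in both arms gave 0.682 against 0.683 with true dates, and 2% on durvalumab only gave 0.669 against 0.682.

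**4. Power, balanced case.** Power = Φ(√(D × 2/3 × 1/3) × |ln HR| − 1.96). With D = 225 and HR 0.68: √50 × 0.3857 − 1.96 = 0.767, power 77.8%. With 2% of events lost, D = 220.5: √49 × 0.3857 − 1.96 = 0.740, power 77.0%. For 200 to 250 deaths and HR 0.65 to 0.72 the loss is 0.3–0.4 points at 1%, 0.6–0.9 at 2% and 1.6–2.2 at 5%.

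**5. OS24.** Under the SAP rule, placebo OS24 is too high by 0.2–0.3 points at 1% undated, 0.5–0.6 at 2% and 1.2–1.6 at 5%.

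**The case against.** The strongest defence is that the rule is prespecified and mechanical, for a group of patients that may be empty. Protocol 8.1.2 requires survival contacts monthly for four months after treatment stops and every two months after that, plus a sweep after each DCO. SAP 3.2.2.1 adds checks of notes, hospital records, general practitioners and death registries. Nothing in the documents suggests that any death will be wholly undated, still less that such deaths will fall in one arm. This stands, and it is why the point is minor.

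A year is also real information, whereas a wholly missing date says nothing about whether death came before the DCO, and SAP 3.2.2.1 censors deaths after the DCO. This stands in part. It justifies censoring when the death is first reported after the DCO. It does not when the report itself is dated on or before the DCO, because the death must then have occurred by the DCO.

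Three stronger readings are tempting, and the documents do not support them.

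- A reader might infer that the SAP contradicts the Protocol's definition of OS. But Protocol 9.5 leaves to the SAP "the procedures to account for missing, unused, and spurious data", and this sentence is such a procedure.
- A reader might infer that no OS analysis with other censoring is planned at all. Table 9 names one; what is missing is a definition that counts these deaths.
- A reader might argue from the rule for adverse events without a start date, "Completely missing: impute first dose date unless the end date suggests it could have started prior to this", that the SAP should likewise keep the death and impute. But SAP 4.1.4 limits that imputation to deciding whether an event is treatment-emergent and derives no durations from it, so it is no precedent for a survival time.

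**Conclusion.** The rule censors some known deaths because they are deaths, and no defined OS analysis counts them. Severity is minor.

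If undated deaths are balanced between arms, the HR is essentially unchanged: it moves by 0.003 or less even at 5% undated. If they occur in one arm only, it moves by roughly the undated share in that arm: about 0.005 to 0.006 at 1%, 0.009 to 0.012 at 2% and 0.024 to 0.032 at 5%, towards durvalumab if they are durvalumab patients and against it if they are placebo patients. A reader might infer from the one-arm rows that the OS result is likely to be biased; the documents give no sign of such an imbalance.

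All of this rests on assumed rates, gaps, follow-up and medians. The text finding in step 1 of the working does not depend on them.

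**What to change.** 1. **Main rule.** Replace the sentence in SAP 3.2.2.1. Where death is evident but undated, and the record that reports it (survival contact, Statement of Death page or registry extract) is dated on or before the DCO, the patient is an OS event at last date known alive + 1. Where that record is dated after the DCO, the patient stays censored at the last known alive date, because death before the DCO cannot be shown. The record date is a mechanical test, which matters because SAP 5.1 has the study unblinded from the PFS analysis.
2. **Count.** Report the number of undated deaths by arm, whatever the date of the reporting record.
3. **Sensitivity, only if there are any.** Define the alternative-censoring row of Table 9 as OS reruns that count all undated deaths as events, once at last known alive + 1 and once at the DCO, shown beside the current censoring rule. Covering all of them matters: the survival sweep follows the DCO (Protocol 8.1.2) and vital status of withdrawn patients is looked up at study end (Protocol 7.3), so many such deaths would be reported too late for the main rule.

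The cost is one SAP sentence, one row of counts and, if needed, a few reruns of the OS model.

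There are two limits. Last known alive + 1 is the earliest possible date. With a 6–24 month gap it puts placebo OS24 too low by 0.16, 0.31 and 0.79 points at 1%, 2% and 5% undated, against 0.23, 0.46 and 1.17 too high under the current rule; with a 0–2 month gap its error is 0.07 points or less. The DCO-dated rerun bounds the other side. Also, the near-recovery of the HR in the table belongs to counting all undated deaths as events. It is closest when the gap is short (within 0.0006 of 0.6187, against up to 0.0074 with a long gap and 5% in one arm). The main rule with its record-date condition was not simulated.

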3.2.2.5 Progression-free survival at 12 (PFS12) and 18 months (PFS18)

The PFS12 and PFS18 will be defined as the KM estimate of PFS (per RECIST 1.1 as assessed by the Investigator) at 12 and 18 months, respectively and both will be obtained using the algorithm described above for the RECIST 1.1 site Investigator tumour data.

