Administration of study treatment (ie, investigational product [IP] durvalumab or placebo) will commence on Day 1 following randomisation to durvalumab or placebo after confirmation of eligibility and will continue on a q4w schedule until confirmed radiological progression, initiation of alternative cancer therapy, unacceptable toxicity, withdrawal of consent, or other reasons which reaching the discontinuation criteria (Section 7.1).

Tumour assessments using computed tomography (CT)/magnetic resonance imaging (MRI) will be performed at the times specified in Table 1 and Table 2. RECIST 1.1 measurements (using BICR assessments) will be used to derive the primary variable of PFS and secondary variables of ORR, DoR, PFS12, and PFS18.

Once a participant has had objective radiological progression recorded and has discontinued study treatment, the participant will be followed up for survival status monthly at the first 4 months, and then every 2 months until death, withdrawal of consent, or the end of the study.

Once the planned statistical analyses have been performed, the analysis portion of the clinical study will have been completed. See Section 4.4 for more information on study completion.

In the event that a roll-over or safety extension study is available at the time of the final data cutoff (DCO) and database closure, participants currently receiving treatment with durvalumab may be transitioned to such a study, and the current study would reach its end. The roll-over or safety extension study would ensure treatment continuation with visit assessments per its protocol. Any participant who would be proposed to move to such a study would be given a new informed consent.

For an overview of the study design see Figure 1, Section 1.3. For details on treatments given during the study, see Section 6.1 Treatments Administered. Guidelines for the management of toxicities are described in Section 8.4.5.

For details on what is included in the efficacy and safety endpoints, see Section 3 Objectives and Endpoints.

4.1.1 Study conduct mitigation during study disruptions due to cases of civil crisis, natural disaster, or public health crisis

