8.1 Efficacy assessments

This study will evaluate the primary endpoint of PFS (mITT). Efficacy assessments of PFS, ORR, DoR, PFS12, PFS18, and time to death or distant metastasis (TTDM) will be derived (by AstraZeneca) using BICR RECIST 1.1 assessments. Time from randomisation to second progression (PFS2) will be assessed by the Investigator according to local standard clinical practice. OS and proportion of participants alive at 24 months from randomisation (OS24) will also be assessed.

Tumour assessments utilise images from CT (preferred) or MRI, each preferably with iv contrast, of the chest and abdomen (including the entire liver and both adrenal glands), collected during part II screening/Baseline and at regular (Follow-up) intervals during the study. Pelvic imaging is recommended only when primary or metastatic disease in the pelvic region is likely. Any other areas of disease involvement should be additionally imaged based on the signs and symptoms of individual participants. It is important to follow the tumour assessment schedule as closely as possible (refer to the SoAs). If an unscheduled assessment is performed (eg, to investigate clinical signs/symptoms of progression) and the participant has not progressed, every attempt should be made to perform the subsequent assessments at the next scheduled visit. Treatment continues until confirmed radiological progression (refer to Appendix E) or other discontinuation criterion (Section 7.1) is met; and scanning/tumour assessments continue until RECIST 1.1-defined radiological progression plus 1 or more additional follow-up scans for confirmation of progression (if clinically feasible). The RECIST 1.1 guidelines (Appendix E) provide a method of assessment of change in tumour burden in response to treatment. Part II screening/baseline imaging should be performed no more than 28 days before start of study treatment, and ideally should be performed as close as possible to and prior to the start of study treatment. The RECIST 1.1 assessments of baseline images identify TLs (defined as measurable) and Non-Target Lesions (NTLs). On-study images are evaluated for TLs and NTLs chosen at Baseline, and for New Lesions (NLs) when they appear. This allows determination of follow-up TL response, NTL lesion response, the presence of unequivocal NLs, and overall timepoint responses (CR, PR, SD, PD, or Not Evaluable [NE]).

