9.4.1.7 Progression-free survival at 12 and 18 months

The PFS12 and PFS18 will be defined as the KM estimate of PFS (per RECIST 1.1 as assessed by BICR) at 12 and 18 months, respectively.

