1.1.2 Secondary objectives

Secondary objectives:	Endpoint/variables:
Key secondary objective: To further assess the efficacy of durvalumab compared with placebo in terms of OS in the mITT	OS
To further assess the efficacy of durvalumab treatment compared with placebo in terms of PFS in all randomised patients (i.e. ITT)	PFS using BICR assessments according to RECIST 1.1 ^a
To further assess the efficacy of durvalumab compared with placebo in terms of OS in the ITT	OS
To further assess the efficacy of durvalumab compared with placebo in terms of: OS24, ORR, DoR, PFS12, PFS18, PFS2 and TTDM in the mITT, and separately in the ITT	OS24 ORR, DoR, PFS12, PFS18 and TTDM using BICR assessments according to RECIST 1.1 ^b PFS2 as defined by local standard clinical practice
To assess the PK of durvalumab	Concentration of durvalumab in blood and non compartmental PK parameters (such as peak

	concentration and trough, as data allow) (sparse sampling)
To investigate the immunogenicity of durvalumab	ADA (confirmatory results: positive or negative; titres [ADA neutralising antibodies will also be assessed])
To assess symptoms and health-related quality of life in patients treated with durvalumab compared with placebo using EORTC QLQ-C30 v3 and QLQ-LC13 in the mITT, and separately in the ITT	Change from baseline in patient-reported symptoms, functioning and global health status/QoL. Time to deterioration in patient-reported symptoms, functioning and global health status/QoL.
To investigate the relationship between a patient's baseline tumour PD-L1 expression and efficacy outcomes with durvalumab compared with placebo in the mITT, and separately in the ITT	IHC analysis of tumoural PD-L1 expression and spatial distribution within the tumour microenvironment relative to efficacy outcomes (OS, PFS, and ORR)

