ADA Anti-drug antibody; BICR Blinded Independent Central Review; DoR Duration of response; EORTC QLQ-C30 European Organisation for Research and Treatment of Cancer 30-item core quality of life questionnaire; IHC Immunohistochemical; ORR Objective response rate; OS Overall survival; OS24 Proportion of participants alive at 24 months from randomisation; PD L1 Programmed death ligand 1; PFS Progression free survival; PFS2 Time from randomisation to second progression; PFS12 Proportion of participants alive and progression free at 12 months from randomisation; PFS18 Proportion of participants alive and progression free at 18 months from randomisation; PK Pharmacokinetic(s); QLQ-LC13 13-item self-administered questionnaire for lung cancer; QoL Quality of Life; RECIST Response Evaluation Criteria In Solid Tumors; TTDM Time to death or distant metastasis;

^a PFS will be based on programmatically derived PFS by BICR assessment according to RECIST 1.1.

^b Analysis of ORR, DoR, PFS12, PFS18 and TTDM will be based on BICR assessment according to RECIST 1.1. See secondary efficacy outcome endpoints [Section 3.2.2](#) and analysis methods [Section 4.2](#) for further details.

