3.2 Outcome variables

All RECIST 1.1 assessments, whether scheduled or unscheduled, will be included in the calculations. This is also regardless of whether a patient discontinues investigational product (IP).

RECIST 1.1 outcomes (i.e. PFS, ORR etc) will be derived using the overall visit responses and relevant dates from the BICR. This will be repeated using the programmatically derived overall visit responses from investigator RECIST 1.1 assessments.

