KM curve along with landmark analyses (i.e. 6 months, 12 months, 18 months, 24 months, 36 months PFS rate) will be presented by treatment arm

The treatment status at progression of patients at the time of analysis will be summarised. This will include the number (%) of patients who were on-treatment at the time of progression, the number (%) of patients who discontinued study treatment prior to progression, the number (%) of patients who have not progressed and were on-treatment or discontinued treatment, and the number (%) of patients who progressed prior to receiving treatment. This will also provide distribution of number of days prior to progression for the patients who have discontinued treatment.

The number of patients prematurely censored will be summarised by treatment arm. A patient would be defined as prematurely censored if they had not progressed (or died in the absence of progression) and the latest scan prior to DCO was more than one scheduled tumour assessment interval plus 2 weeks (10 weeks if period between randomisation and DCO for that patient is 48 weeks or less; 14 weeks otherwise) prior to the DCO date.

Additionally, summary statistics will be given for the number of days from censoring to DCO for all censored patients.

A summary of the duration of follow-up will be summarised using median time from randomisation to date of censoring (date last known to have non-progression) in censored (not progressed) patients only, presented by treatment group.

Additionally, summary statistics for the number of weeks between the time of progression and the last RECIST 1.1 assessment prior to progression will be presented for each treatment group.

Summaries of the number and percentage of patients who miss two or more consecutive RECIST 1.1 assessments will be presented for each treatment group.

All collected RECIST 1.1 data will be listed. In addition, a summary of new lesions (i.e., sites of new lesions) will be produced.

Sensitivity Analyses

The following sensitivity analyses will be performed:

1. Evaluation-time bias

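### SAP 3.2.2.5 takes PFS12 and PFS18 from Investigator reads, while the protocol and the SAP's own objectives specify BICR

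*SAP*

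**What the plan says.** The derivation section for these endpoints, SAP 3.2.2.5, reads: "The PFS12 and PFS18 will be defined as the KM estimate of PFS (per RECIST 1.1 as assessed by the Investigator"). The rest of the sentence says that both rates come from applying the PFS algorithm to the site Investigator tumour data, so the source is named twice.

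The protocol gives a different source. Section 9.4.1.7 defines the two rates as the "KM estimate of PFS (per RECIST 1.1 as assessed by BICR"). Section 4.1 says "RECIST 1.1 measurements (using BICR assessments) will be used to derive the primary variable of PFS and secondary variables of ORR, DoR, PFS12" and PFS18. Section 8.1 says "PFS12, PFS18, and time to death or distant metastasis (TTDM) will be derived (by AstraZeneca) using BICR RECIST 1.1 assessments". The synopsis, the Section 3 objectives table and Section 9.4.1.1 agree.

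The SAP's own objectives follow the protocol. The table in 1.1.2 lists "ORR, DoR, PFS12, PFS18 and TTDM using BICR assessments according to RECIST 1.1", for the mITT and separately the ITT. Footnote b adds: "Analysis of ORR, DoR, PFS12, PFS18 and TTDM will be based on BICR assessment according to RECIST 1.1".

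**The concern.** The protocol definition and SAP 3.2.2.5 are worded almost identically except for the reader. A programmer working from the derivation section would use Investigator reads; one working from the objectives table would use BICR.

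The choice matters by the SAP's own account. Section 3.1.2 makes BICR primary for efficacy, and Section 4.2.1 uses Investigator-based PFS to assess ascertainment bias. Under 3.2.2.5 as written, a named secondary endpoint would rest on the sensitivity source.

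The results could also disagree with each other. SAP 4.2.1, whose main analysis uses BICR data, plans a KM curve with "landmark analyses (i.e. 6 months, 12 months, 18 months, 24 months, 36 months PFS rate) will be presented by treatment arm". The report could then show two different 12-month PFS rates for the mITT, with the Investigator one carrying the PFS12 label.

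**Working it through.** No design figure for PFS12 or PFS18 is given, so the main check is a comparison of the current texts.

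**Which reader each place names for PFS12/PFS18**

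- BICR, protocol (six places): synopsis objectives, Section 3, 4.1, 8.1, 9.4.1.1, 9.4.1.7.
- BICR, SAP (two places): the 1.1.2 table and its footnote b.
- Investigator (one place, named twice in one sentence): SAP 3.2.2.5.
- No reader named: SAP 4.2.2.5, which refers to the OS24 method, and the PFS12/PFS18 row of SAP Table 9.

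**General rules.** SAP 3.2 says "RECIST 1.1 outcomes (i.e. PFS, ORR etc) will be derived using the overall visit responses and relevant dates from the BICR", then repeated on Investigator data. SAP 3.1.2 makes BICR primary. Neither mentions PFS12 or PFS18.

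**Neighbouring endpoints.** SAP 1.1.2 groups ORR, DoR and TTDM with PFS12 and PFS18. Their derivation sections (3.2.2.3, 3.2.2.4, 3.2.2.6) all name BICR. Section 3.2.2.5 is the exception in its group.

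**Declared changes.** SAP Section 6 lists two: PRO time to deterioration as an added secondary endpoint, and the removal of biopsy from the TTDM definition. The SAP amendment history records no edit to 3.2.2.5.

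**Count of affected estimates.** 2 time points × 2 arms × 2 populations = 8. The 4 mITT estimates have landmark counterparts in SAP 4.2.1. That landmark sentence is not stated to be repeated on the ITT, whereas 4.2.2.5 does repeat PFS12 and PFS18 there. So the analysis text gives no BICR rate at these times for the 4 ITT estimates.

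**Illustration of size (assumption only).** Inputs: the median PFS values of 16.8 and 5.6 months that protocol 2.3.1 cites from the earlier trial. Assumptions: exponential PFS, and an Investigator hazard equal to k times the BICR hazard. Then S(t) = exp(−ln 2 × t × k / median). For example, at a median of 16.8 months, t = 12 and k = 1, exp(−0.6931 × 12 / 16.8) = exp(−0.495) = 61.0%.

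| Median (months) | t (months) | k = 1 | k = 0.9 / 1.1 | k = 0.8 / 1.2 |
|---|---|---|---|---|
| 16.8 | 12 | 61.0% | 64.0% / 58.0% | 67.3% / 55.2% |
| 16.8 | 18 | 47.6% | 51.3% / 44.2% | 55.2% / 41.0% |
| 5.6 | 12 | 22.6% | 26.3% / 19.5% | 30.5% / 16.8% |
| 5.6 | 18 | 10.8% | 13.5% / 8.6% | 16.8% / 6.9% |

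The absolute shifts from k = 1, taken before rounding, run from 2.2 to 3.7 points for a 10% hazard difference and from 3.9 to 7.8 points for 20%.

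**The case against.** The contradiction itself is hard to dispute; the case on the other side concerns its consequences.

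- *The general rules already ask for BICR.* Under SAP 3.2 both versions would be derived, so the likely harm is a wrong version under the PFS12 and PFS18 labels rather than a lost BICR estimate. This limits the effect. It does not resolve the conflict, because 3.2.2.5 is specific to these endpoints and names only Investigator data.
- *BICR rates for the ITT are planned elsewhere.* SAP 1.1.2 lists both endpoints by BICR for the ITT, and 4.2.1 repeats the BICR KM plot on the ITT, from which the two rates could be read. This stands. The ITT gap is confined to the analysis text, where no sentence repeats the landmark rates on that set.
- *Nothing shows a deliberate change.* Leftover wording fits the text equally well, and one would not expect Section 6 to list that. Intent cannot be established, but the correction is needed either way.
- *The numerical illustration is not evidence of a difference.* The values of k have no source in the documents, and the medians come from a trial of concurrent chemoradiation patients only, whereas this trial also enrols sequential ones. This stands: the figures show only what an assumed difference would do.
- *The endpoints are descriptive.* This stands too, and it caps the importance of the point.

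**Conclusion.** The concern holds. The text of SAP 3.2.2.5 is wrong when set against the protocol and SAP 1.1.2, and no change of reader is declared. It should be fixed.

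The reach is limited. PFS12 and PFS18 are summarised by arm from the KM curve without a between-arm test (protocol 9.5.1.6) and lie outside the testing sequence (protocol 9.1). Type I error, power, the primary PFS test and OS do not depend on them. What is at risk is the agreement of eight reported estimates with their stated definition and with the primary BICR curve. The actual size depends on reader disagreement in this trial, which the documents do not give and which could be nil. The conclusion rests on the text comparison, not on the illustrative shifts.

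**What to change.** In SAP 3.2.2.5, make BICR the assessor and have the closing clause point to the Section 3.2.1 algorithm applied to BICR data. Name BICR in 4.2.2.5 and in the PFS12/PFS18 row of Table 9. Label any Investigator version as a sensitivity output.

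If Investigator reads were intended, state and justify this in SAP Section 6 as a departure from the protocol, and correct the 1.1.2 table and footnote b.

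The cost of the first route is one corrected sentence and two reader labels. No new data or analyses are needed.
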